2. HYPOTHESIS AND OBJECTIVES

Specific aim 1: To assess the effectiveness of MPI, versus standard care, in improving adherence to IVT follow-up appointments at 6, 12 and 18 months (main timepoint for primary outcome) *in patients with nAMD and DME requiring long term management* (primary outcome).

Hypothesis 1: *Compared to those in standard care, patients in the MPI group will have higher adherence to long-term follow-up appointments and IVT therapy.*

Specific aim 2A: Assess the effectiveness of MPI, versus standard care, in improving domain-specific CAT scores at the various follow-up timepoints (secondary outcome).

Hypothesis 2A: *Compared to those in standard care, patients in the MPI group will have greater gains in domain-specific CAT scores at each follow-up time point.*

Specific aim 2B: Assess the effectiveness of MPI versus standard care in improving visual acuity (VA), contrast sensitivity (CS), disease free intervals between IVT (as measured on optical coherence tomography (OCT) (secondary outcomes).

Hypothesis 2B: *Compared to those in standard care, patients in the MPI group will have greater VA and CS gains and achieve longer disease-free intervals between IVT at each follow-up time point.*

Specific Aim 3: To assess implementation outcomes of the MPI such as acceptability, adoptability, appropriateness, feasibility, fidelity.

Hypothesis 3: *Using a mixed methodology, with quantitative and qualitative outcome measures as reported by patients, caregivers, clinicians, nurses and allied health professionals, MPI will be an appropriate, adoptable, acceptable, feasible intervention with good fidelity.*

Specific Aim 4: To assess the cost-effectiveness of the MPI for improving adherence to IVT, considering its potential impact on long term visual acuity (VA) loss and QoL adjusted years (QALYs)

Hypothesis 4: *The MPI is incrementally cost-effective relative to standard care, based on accepted willingness-to-pay thresholds⁴².*

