- Following baseline assessment, **participants with suboptimal CAT scores (Cohort 1-<50 in any domain)** will be included in the RCT and randomly allocated in a 1:1 ratio to either the intervention group (personalised multi-disciplinary protocolised intervention, MPI) or the control group (standard care). Randomisation will be conducted using a computer-generated random sequence created by an independent biostatistician not involved in recruitment or outcome assessment. To ensure balance across disease types, randomisation will be stratified by diagnosis (neovascular age-related macular degeneration [nAMD] vs. diabetic macular edema [DME]). Allocation concealment will be maintained using sequentially numbered, opaque, sealed envelopes prepared by an independent study coordinator. The envelopes will only be opened after baseline data collection to assign participants to their respective groups. Co-Is that are not treating clinicians and data analysts will remain blinded to group allocation, although masking of participants and principal investigator and Co-Is who are the treating clinicians will not be feasible due to the nature of the intervention.

- For the MPI arm, the CAT scores integrated into the electronic medical records will be used to formulate **an automated protocolized standardized MPI for all patients based on the domain specific scores that are sub-optimal** (See **Table 2**). All MPI patients will receive *a medical consultation (compulsory) and an addition of Intervention 1-4 (electives, 1) NE, 2) OP, 3) OT, 4) SW*. In the MPI arm, these referrals would be automatically triggered by the study team based on baseline CAT scores and the treating clinician will be informed. The MPI visits will take place on the same day as standard clinical visits where possible, however additional MPI study visits may be needed if there are scheduling challenges. Referral adherence to the MPI appointments and intervention will be assessed.

Sub-optimal scores are defined as any domain where the scores are below 50 at baseline or have reduced by 25% from the baseline visit. Table 2 summarizes the MPI interventions that are relevant to each CAT domain. A tailored MPI will be formulated and recommended to the patient at baseline, or at a follow-up time-points where domain scores decrease, and the MPI should be completed within 4 months.

Table 2: Standardised personalised MPI based on sub-optimal CAT domain-specific scores

| Ret CAT | | MacCAT | |

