At each follow up time point, based on the previous scheduled follow-up appointments and recommended IVT schedule, the study team will assess if the patient has been “adherent” or “non-adherent”. If the patient does not visit the clinic within the range of the follow-up time points or does not attend the scheduled study visit, phone calls will be made to determine reasons or barriers for adherence. A remote invitation to complete the CAT questionnaire will also be sent to these patients or if uncontactable, they will be approached and interviewed at their next clinical visit. For previously treated patients, previous adherence status up to 2 years prior to study enrolment for the time of IVT treatment will be recorded by the study team from medical records.

Secondary outcome measures will be assessed at baseline and 6, 12, and 18 month follow up visits (+/- 8 weeks) including:

- CAT scores (Specific aim 2A) from the CAT questionnaire database
- Visual function -Monocular and binocular presenting corrected VA and CS (Specific aim 2B) will be collected from the clinical records. If data are not present, the CRCs will conduct these tests on participants using standardized protocols.
- Disease free intervals as defined by the maximum IVT treatment interval where no disease activity recurrence is detected on OCT will be collected from clinical records and OCT images from the clinical database (Specific aim 2B)
- Tertiary outcome measures include the acceptability, adoptability, appropriateness, feasibility, fidelity through mixed method testing with interviews and questionnaires (Specific aim 3).
- The costs of MPI, baseline and 18-month assessment of Euro-quality of life (EQ-5D) to assess QALYs (Specific aim 4)

Qualitative and quantitative analysis of key stakeholders (Specific aim 3)

The PI, assisted by their Co-Is and collaborators, will identify eligible individuals for qualitative interviewing that will be performed with major stakeholders between 6 to 15 months timeline. These include the clinicians, nurses and the allied health specialists (OP, OT and SW) who will be involved in administering the MPI, and patients and care-givers who receive the MPI. Potential individuals will be contacted over email or phone call, and a trained study team will follow up on affirmative responses by obtaining written informed consent to carry out the following study procedures:

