8. SAMPLE SIZE AND STATISTICAL METHODS

8.1. Determination of Sample Size

Specific Aim 1 and 2: The primary outcome comparison of adherence rates to IVT treatment between the MPI arm versus standard care at various follow-up time points with 18 months as the main time point. It is estimated that the baseline non-adherence rate with standard care arm is 40% (SD=2). Considering a reduction of the non-adherence rate to 20% as a clinically significant difference, and assuming a power of 80% and a two-sided level of significance at 5%, the minimum sample size

required is 79 patients per arm (rounded up to 160 patients in total). Assuming a maximum 20% dropout in the study we estimate a sample size of 200 patients (Specific aim 1).

For secondary outcomes such as the improvement of QoL as assessed by the various CAT domain scores, we assume a modest effect size difference of 0.5 between the two arms. Using a power of 80%, a two-sided level of significance at 5%, and the maximum 20% dropout rate, we estimate the required sample size is 158 (79 per arm) (Specific aim 2A). Hence, this is included in the larger sample size calculated above.

Specific aim 3: There is no *a priori* sample size required for qualitative interviews. We will continue our semi-structured interviews until thematic saturation is reached (i.e. no new themes emerge). Based on previous studies by our group^{31,67}, we anticipate the need to interview between 5-10 participants for each stakeholder group to obtain data saturation, broadly: (a) clinicians using CATs and MPI, (b) NE, OP, OT and SW involved in administering MPI (c) patients involved in this study, and (d) caregivers of patients. For the purposes of estimating a budget for this grant proposal, we state an indicative sample size of 40 interview participants i.e. 10 in total for stakeholder group a and b, and 30 for stakeholder group c and d (patients and caregivers).

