8.2. Statistical and Analytical Plans

Specific aim 1: Planned statistical analysis for the primary outcome measure will be the difference in percentage of adherence rate between the standard care and MPI arm assessed by the chi-square test or Fisher's exact test. Cox proportional hazards model will be used to assess the independent effect of MPI on adherence rates, after adjusting for age, baseline CAT scores, visual function, anatomical outcomes, type of IVT medication given, and disease-free intervals.

Specific aims 2A and 2B: CAT scores will be assessed with a two-sample t-test to compare the differences in mean CAT scores between the 2 arms. Linear mixed models will be used to assess the independent effect of MPI on follow-up CAT scores, after adjusting for fixed effects terms such as age, baseline CAT scores, visual function, anatomical outcomes, type of IVT medication given, and disease-free intervals, and a random slope term follow-up time (measured in months).

Specific aim 3 Interviews will be conducted in-person or online, audio-recorded, and transcribed verbatim by professional transcribers (i.e. transcriptions outsourced to third party). Designated researchers in the study team will check a random 10% sample of interview transcriptions for accuracy, prior to qualitative data analysis. If errors or inaccuracies are found in the random sample of transcripts, then 100% of the transcripts will need to be checked and edited for accuracy, prior to data analysis. We will analyse the qualitative data as per Gale et al's thematic analysis⁶². NVivo software will be used to manage qualitative data analysis. A standardised questionnaire to assess implementation outcomes will also be administered to all the stakeholders for a quantitative assessment.

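### Aim 2A pairs an unadjusted t-test with a mixed model whose covariates may be post-randomisation and does not say which decides; a clean baseline-adjusted comparison would be more precise at almost no cost

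*Protocol*

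**What the plan says.** Hypothesis 2A (protocol section 2) holds that "patients in the MPI group will have greater gains in domain-specific CAT scores at each follow-up time point". Section 5 gives the schedule: "Secondary outcome measures will be assessed at baseline and 6, 12, and 18 month follow up visits (+/- 8 weeks) including" the CAT scores. Every patient therefore has a baseline score, and that score also decides entry to the randomised part, because Cohort 1 requires a score below 50 in at least one domain. Patients are "randomly allocated in a 1:1 ratio", stratified by diagnosis but not by CAT score.

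Section 8.2 gives two between-arm analyses for Aim 2A:

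- First, "CAT scores will be assessed with a two-sample t-test to compare the differences in mean CAT scores between the 2 arms". The sentence does not mention baseline and does not say whether the score is the follow-up level or the change.
- Second, a linear mixed model for the independent MPI effect on CAT scores after baseline. Its fixed effects include baseline CAT, age, visual function, anatomical outcomes, the IVT drug and the disease-free interval, and it has a random slope for time.

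Neither is named as the analysis that decides the aim, and diagnosis is not among the terms listed for either.

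Section 8.1 sizes Aim 2A as follows: "we assume a modest effect size difference of 0.5 between the two arms". At 80% power, a 5% two-sided level and an allowance for 20% dropout, it arrives at 158 patients, 79 per arm.

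**The concern.** The hypothesis is about improvement, and the most useful predictor of a later CAT score, the same patient's baseline score, is already in hand. The first-named test leaves it out. If that test is run on follow-up scores, any chance baseline difference between the arms in a domain passes in part into the reported MPI effect, and the standard error is larger than the data require. With up to eight domains per instrument and no stratification on CAT score, some chance differences are to be expected.

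The mixed model would normally settle this, but its other covariates cloud it. Disease-free interval is itself an Aim 2B outcome. Section 1 says that the MPI consultation discusses the choice of IVT drug and longer treatment intervals. If these covariates are measured after randomisation, adjusting for them can remove part of the effect that the trial wants to estimate. As written, the sponsor can report an unadjusted comparison or a possibly over-adjusted one, and nothing says which comes first.

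**Working it through.** **Inputs from section 8.1.** Standardised effect 0.5; two-sided 5%; power 80%; dropout 20%; Aim 2A size 158 (79 per arm). For the trial as a whole: "Assuming a maximum 20% dropout in the study we estimate a sample size of 200 patients". Allocation is 1:1 (section 5).

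**Assumption.** The correlation r between baseline and follow-up CAT score is not in the protocol. I use 0.3, 0.5 and 0.7.

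**Step 1: reproduce the plan's figure.** With the normal approximation, n per arm = 2(z₀.₉₇₅ + z₀.₈₀)²/d² = 2(1.960 + 0.842)²/0.25 = 62.8, so 63. Dropout: 63/0.8 = 78.75, so 79 per arm; 126/0.8 = 157.5, so 158 in total. This matches exactly. The t-based version gives 63.8, so 64 per arm. The stated size is therefore that of an unadjusted two-sample comparison.

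**Step 2: evaluable numbers.** 200 × 0.8 = 160, or 80 per arm, if all 200 are randomised. The stand-alone Aim 2A calculation needs 64 per arm.

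**Step 3: power with baseline adjustment.** Analysis of covariance multiplies the SD by √(1 − r²), so the effective d is 0.5/√(1 − r²): 0.524, 0.577 and 0.700 for r = 0.3, 0.5 and 0.7. The noncentrality is d√(n/2). Noncentral t power, two-sided 5%:

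| Evaluable per arm | Unadjusted | r = 0.3 | r = 0.5 | r = 0.7 |
|---|---|---|---|---|
| 80 | 88.2% | 90.9% | 95.2% | 99.3% |
| 64 | 80.2% | 83.7% | 90.0% | 97.6% |

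The gain is about 3, 7 and 11 points at 80 per arm, and about 4, 10 and 17 points at 64 per arm.

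**Step 4: would a t-test on change do instead?** Its SD is multiplied by √(2(1 − r)). With the effect of 0.5 in units of the follow-up SD, power at 80 per arm is 75.7%, 88.2% and 98.2% for r = 0.3, 0.5 and 0.7. At 64 per arm it is 66.0%, 80.2% and 95.2%. Change scores therefore lose power below r = 0.5 and gain nothing at 0.5. Because 1 − r² = (1 − r)(1 + r) ≤ 2(1 − r), baseline adjustment is never less precise than change, apart from the degree of freedom it uses.

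**Step 5: chance imbalance.** The standard error of a baseline mean difference is √(2/n): 0.158 SD at 80 per arm and 0.177 SD at 64. A t-test on follow-up scores carries r times the imbalance. At 80 per arm and r = 0.5, a one-standard-error imbalance moves the estimate by 0.5 × 0.158 = 0.079 SD, which is 16% of the 0.5 target (0.079/0.5). On change scores the carried share is r − 1, here the same size with the opposite sign.

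**The case against.** The strongest reply is that the plan already adjusts for baseline: the sentence after the t-test sets out a mixed model with baseline CAT as a fixed effect. That is correct, and a reader who inferred that the plan ignores baseline would be wrong. What it leaves open is the rest of the covariate list, which is not confined to values before randomisation, and which of the two analyses leads.

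Second, the t-test sentence may mean change scores, which would fit the hypothesis. The text allows this, so it should not be said as fact that raw follow-up means are compared. Step 4 shows that change scores would not recover the precision unless r exceeds 0.5.

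Third, a reader might infer bias or an underpowered aim. The documents support neither. In a 1:1 randomised trial the unadjusted comparison is unbiased on average, and it has 80% power at 64 per arm and 88% at 80. A flat loss of 10 points is not supported either: it needs r = 0.5 and 64 per arm, and the same r gives about 7 points at the planned 80.

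Fourth, the lead analysis for a secondary endpoint is often settled in a statistical analysis plan, which is not shown here. That limits the weight of the point. It does not remove it, because the protocol itself fixes the t-test and the covariate list.

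Last, adjustment needs a definition of baseline. Section 5 lets Cohort 2 patients be randomised later, once a score has fallen below 50 or by 25%. Their enrolment score and their score at randomisation then differ by construction. This objection stands and has to be answered in the fix.

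**Conclusion.** The point holds as one of efficiency and clarity for a secondary outcome. Section 8.2 offers an unadjusted t-test and a mixed model with covariates of unstated timing, names neither as decisive, and so lacks a clean baseline-adjusted randomised comparison of CAT scores. Adjustment would add about 3 to 11 points of power at 80 evaluable per arm, and about 4 to 17 points at 64, for r between 0.3 and 0.7. It would also take chance baseline imbalance out of the estimate.

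These figures rest on the assumed r, on the protocol's effect size of 0.5 read in units of the follow-up SD, on all 200 patients being randomised (for the 80 per arm), and on a domain scored in every evaluable patient. A domain found in only one of the two instruments would have fewer. That the mixed model over-adjusts is a possibility rather than a finding, since the protocol does not say when those covariates are measured.

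**What to change.** In section 8.2:

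- Name one baseline-adjusted comparison as the Aim 2A result: either analysis of covariance at 6, 12 and 18 months, or the mixed model with an arm-by-visit term. The terms are arm, that domain's baseline score and diagnosis.
- Restrict any further covariates to values measured before randomisation.
- Report the adjusted mean difference at each visit with its 95% CI.
- Define baseline as the last score before randomisation, including for patients randomised later from Cohort 2.
- Keep the two-sample t-test as descriptive.

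The cost is a few sentences. Baseline CAT scores and diagnosis are already collected, the two adjustment terms use two degrees of freedom, and the sample size need not change.

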|---------------------|---------------|---------------------|---------------|
| Item Bank | Interventions | Item Bank | Interventions |
| Visual symptoms | (2) | Activity Limitation | (2), (3) |
| Activity Limitation | (2), (3) | Lighting | (2) |
| Emotional | (1), (4) | Emotional | (1), (4) |
| Health Concerns | (1), (4) | Concerns | (1), (4) |
| Convenience | (1), (4) | AMD management | (1), (4) |
| Lighting | (2), | | |
| Social | (4) | | |
| Economic | (4) | | |

- In the standard care arm, the treating clinician will be masked from the CAT scores and will use his/her own discretion when recommending the treatment regimen or when making any appropriate nurse or allied health referrals, independent of the CAT scores. The CAT scores will be recorded by the clinical research coordinator at baseline and follow-up visits for comparison to the MPI arm.
- For those patients who do not have sub-optimal CAT scores at baseline, they will be assigned to an observational study group (Cohort 2) to continue to undergo routine clinical care and at the assigned study time points, they will be reassessed for any changes in their CAT scores and will undergo randomisation into the RCT if their scores have dropped below 50 or have reduced by 25% from the baseline visit. For those patients who do not experience sub-optimal CAT scores or a significant drop in their CAT scores during the duration of the study, they will still have their data collected at

all study visits based on the protocol but will not undergo randomisation. If any of these cohort patients show non-adherence to clinic visits during the duration of the study, they will be eligible for “rescue” MPI according to the clinician’s discretion at their next study visit and will be analysed as a separate sub-group.

Study schedule and outcome measures

The primary outcome is the comparison of adherence rates to IVT treatment between the MPI arm versus standard care (Cohort 1) at 6, 12 and 18 month time points (+/- 8 weeks) (main outcome) (Specific aim 1). The follow-up study visits will be coordinated with the planned clinical standard care visits, only if the patient does not have a routine clinical care visit scheduled within the range of the follow-up time-points will an additional study visit be scheduled.

Adherence is defined as

- 1) patient attends all follow-up appointments within 1 month of the planned follow up date, and
- 2) patient receives IVT within 1 month of when the doctor recommends IVT.

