Specific aim 4: To assess the cost-effectiveness analysis of the MPI, we will develop a cohort-based Markov model embedded within a decision tree to simulate the net lifetime cost and effectiveness of the MPI compared to standard care. The model's health states will be defined by VA ranges, consistent with prior cost-effectiveness studies for of macular disease treatments^{63,64}. We will quantify the incremental costs of implementing the MPI using an activity-based costing approach, which includes all non-sunk costs – such as labour, materials and supplies, and amortized technology and rental costs – associated with treating each patient. These costs will be categorized by key activities, including physician/nurse/allied health training, CAT assessment, and referral to personalized programs. Treatment costs will be based on non-subsidized bill sizes, which are expected to approximate actual costs. Data on health resource utilization and costs incurred during the first 18 months will come from this study. For benefits, which are measured in terms of QALYs gained, QoL weights will be measured for month 18 using the EQ-5D instrument and validated local preference weights⁶⁵. The key difference between the MPI and standard care will be the proportion of IVT-adherent patients, influencing costs and long-term VA outcomes. As these differences likely persist over a patient's remaining lifetime, the model will extrapolate long-term VA and corresponding quality-of-life weights based on published trajectories for treated (adherent) and untreated (non-adherent) patients⁶⁶. With each subsequent annual cycle, the surviving cohort will accrue costs and QALYs associated with their VA and IVT adherence status. This model will be used to estimate the incremental cost-effectiveness ratio (ICER) for the MPI. We will also conduct one-way and n-way sensitivity analyses for all key model inputs and present cost-effectiveness acceptability curves showing the probability that the MPI is cost-effective at various willingness-to-pay thresholds policymakers may consider. We will also conduct scenario analyses to investigate the robustness of our results to alternative assumptions on long-run VA trajectories.

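### The cost-effectiveness model gives every non-adherent patient the untreated vision trajectory, although one late visit or injection makes a patient non-adherent; modelled QALY gains are overstated if such patients keep any treatment benefit

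*Protocol*

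**What the plan says.** Section 5 of the Protocol (study schedule and outcome measures) sets two conditions for adherence, and both must be met: "patient attends all follow-up appointments within 1 month of the planned follow up date", and "patient receives IVT within 1 month of when the doctor recommends IVT". Failing either one once is enough to be non-adherent.

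Section 8.2, Specific aim 4, then uses this binary status as the driver of the Markov model: "The key difference between the MPI and standard care will be the proportion of IVT-adherent patients". Long-run VA and the matching quality-of-life weights are extrapolated "based on published trajectories for treated (adherent) and untreated (non-adherent) patients". The reason given for carrying the contrast forward is: "As these differences likely persist over a patient's remaining lifetime". In each later annual cycle, costs and QALYs both depend on VA and adherence status.

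The trial itself supplies resource use and costs for the first 18 months, and EQ-5D weights at month 18. The same section plans sensitivity analyses on the key model inputs and scenario analyses on long-run VA.

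**The concern.** Non-adherent means at least one lapse of more than a month in section 5, and untreated in section 8.2. These are different groups. Section 1 attributes poorer real-world results mainly to fewer injections being given, which is under-treatment rather than no treatment.

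The trial's adherence difference is therefore multiplied by a treated-versus-untreated contrast that the adherence definition does not create. Hypothesis 4, that MPI is incrementally cost-effective, rests on the QALYs and costs that come out of this step. The randomised comparison of adherence is not affected.

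**Working it through.** **Plan's own figures.** The Protocol states no QALY gain or ICER, so none can be reproduced. The adherence contrast that feeds the model is the planning one in section 8.1: 40% non-adherent under standard care against 20% under MPI. The sample size built on it reproduces with unpooled variance: (1.960 + 0.842)² × (0.40×0.60 + 0.20×0.80) / 0.20² = 78.5, so 79 per arm. Rounding to 160 and allowing 20% dropout gives 160/0.8 = 200, as stated.

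**Effect on QALYs.** Let G be the QALY gap between the treated and untreated trajectories after month 18, and f the share of G that patients classed as non-adherent really lose. Neither is in the documents. Then

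incremental QALYs = (0.40 − 0.20) × G × f.

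The plan sets f = 1, giving 0.20 G, so its overstatement factor is 1/f.

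| f (assumed) | QALY gain | Overstatement by the plan |
|---|---|---|
| 1 (plan) | 0.20 G | 1 |
| 0.75 | 0.15 G | 1.33 |
| 0.50 | 0.10 G | 2 |
| 0.25 | 0.05 G | 4 |

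f can be built from two assumed parts: a share s of the non-adherent who stop entirely, and a fraction r of the benefit kept by the others, with f = s + (1 − s)(1 − r). For s = 0.25 and r = 0.8, f = 0.25 + 0.75×0.2 = 0.40 (2.5 times). For s = 0.5 and r = 0.5, f = 0.5 + 0.5×0.5 = 0.75 (1.33 times).

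**How treated can a non-adherent patient be?** This is an illustration only. Assume k visits in 18 months, and that the 40% applies to the all-visits rule over that period. With independent visits, the chance that a given visit is late is q = 1 − 0.60^(1/k), and the mean number of late visits among the non-adherent is kq/0.40.

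| k | q | Mean late visits | Share on time |
|---|---|---|---|
| 6 | 8.2% | 1.22 | 80% |
| 9 | 5.5% | 1.24 | 86% |
| 12 | 4.2% | 1.25 | 90% |
| 18 | 2.8% | 1.26 | 93% |

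Lapses probably cluster within patients. A beta-binomial model with k = 12 and the same 40% gives:

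| Intraclass correlation (assumed) | Late visits of 12 | Share on time |
|---|---|---|
| 0.3 | 3.17 | 74% |
| 0.5 | 4.7 | 61% |
| 0.7 | 6.9 | 43% |

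The group's mix thus depends heavily on clustering, but in none of these cases is it an untreated group.

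**Effect on the ICER.** Let C be the MPI cost per patient and D the treated-minus-untreated cost gap. The planned ICER is (C + 0.20 D)/(0.20 G) = (5C + D)/G.

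- If costs and QALYs shrink by the same f, the corrected ICER is (5C/f + D)/G. This is higher, so the plan looks too favourable.
- If the true cost gap is 10% and the true QALY gap 25% of those modelled (assumed), the corrected ICER is (C + 0.02 D)/(0.05 G) = (20C + 0.4 D)/G. The planned value is then too high whenever 5C + D > 20C + 0.4 D, that is, C < 0.04 D.

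The sign depends on quantities that the documents do not give.

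**The case against.** **ICER direction.** A reader might infer that the ICER is biased towards MPI being cost-effective. The documents do not support this. Costs also follow adherence status, so costing non-adherent patients as untreated may overstate the incremental injection cost too, and the algebra above shows that the net bias can go either way. This objection stands and limits the point to QALYs.

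**Size.** A reader might take the on-time shares as bounds. They are not: the visit count and clustering are assumed, and patients who stop attending are an extreme form of clustering. Section 8.1 does not say that its 40% was derived under the all-appointments rule, and section 5 does not say whether status at month 18 is cumulative. This also stands. One late visit within whatever window is assessed still suffices.

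**Planned mitigation.** Sensitivity analyses on all key inputs and scenarios on long-run VA could include under-treatment, and nothing excludes starting from VA observed at month 18. This softens the problem. But no scenario is said to separate delayed or partial treatment from none, and the treated/untreated mapping is the only main assumption stated.

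**Acceptability curves.** The Protocol says: "We will also conduct one-way and n-way sensitivity analyses for all key model inputs and present cost-effectiveness acceptability curves". A reader might infer that these curves cannot be produced without a named probabilistic analysis. Promising a probability already implies one, and its details may properly sit in an analysis plan that is not shown. This is no defect.

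**Persistence.** Lifetime persistence is offered as likely, and it governs only the period after month 18. Imposing a waning effect, or scaling vision loss by the share of injections received, would be a modelling preference rather than a correction.

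**Conclusion.** The point holds for QALYs. Sections 5 and 8.2 use non-adherent for two different groups, and following the stated mapping overstates the modelled QALY gain whenever patients with a lapse keep some treatment benefit. The factor is 1/f: 1.33 to 4 for assumed f from 0.75 to 0.25. The documents give neither f nor G, so this is a range and not an estimate. The overstatement disappears only if non-adherent patients as a group lose the whole treated-minus-untreated gap (f = 1).

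A bias of the ICER in favour of MPI is not established. The matter concerns Specific aim 4 only and should be settled before the model is built.

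**What to change.** In section 8.2, Specific aim 4:

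1. Define the model's adherence states by treatment actually received to month 18, for example on schedule, delayed or under-treated, and discontinued.
2. Start the extrapolation from the VA observed at month 18.
3. In the main analysis, apply the untreated trajectory only to patients who have discontinued injections.
4. Assign costs by the same states, so that costs and QALYs change together.
5. Report the present mapping, with all non-adherent patients untreated for life, as a bounding scenario.

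No new patient data are needed: VA is collected at 6, 12 and 18 months, and attendance and injections are already checked against the recommended schedule to classify adherence. The cost is extra model work and an under-treated trajectory that must be justified and varied in sensitivity analysis.
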